6.1 Safety Monitoring Analysis

The IDMC will review quarterly descriptive summaries of accumulating participants' disposition and safety. The analyses will be conducted by unblinded supporting staff independent from the study team. The investigators/site personnel, CRO and sponsor team will remain blinded, except for a dedicated unblinded statistical team at the CRO that is preparing analyses for the IDMC.

The primary intent of these analyses is the patient safety monitoring. IDMC may recommend change or early stop of the study in case of safety issue.

Details on outputs used to support the review by the IDMC are available in the IDMC TFL shell document.

^a Power estimations are based on an assumed HR=0.73 for EFS and a HR=0.75 for OS and the prerequisite that the EFS null hypothesis can be rejected at either IA or PA. Futility-bounds are non-binding.

6.2 Interim Analyses

A first interim analysis is planned once 279 EFS events as assessed by the BIRC (65% of EFS events required for the primary analysis) across both arms are observed. The number of EFS events as assessed by the BIRC will be monitored throughout the study. The cutoff date will be determined prospectively based on an event projection as the date when approximately 279 events will be reached. In case it turns out at the time of the EFS IA1 database lock that the observed number of EFS events is >3.5% below the planned number (<270), the IA cut-off date will be revised prior to the conduct of the analysis, based on blinded information on the number of EFS events only, to include at least 270 events in the IA dataset. The second interim analysis will be triggered once 85% of the total number of events (365 events) are observed or one year after the first interim analysis, whichever occurs first. The corresponding cutoff date will be re-evaluated based on event projections.

The interim analyses will be conducted for the IDMC by unblinded supporting staff independent from the study team and will focus on primary and selected secondary efficacy endpoint analyses. The Investigators/site personnel, Sponsor team and CRO will remain blinded, except for a dedicated unblinded statistical team at the CRO that is preparing analyses for the IDMC.

The main intent of these analyses is to demonstrate that xevinapant + CRT prolongs EFS as assessed by the BIRC versus placebo + CRT. No early stopping for superiority of efficacy is planned. Provided that EFS interim analysis results are positive, the data might be used for regulatory and health technology assessment submission purposes, in case of which the CRO and Sponsor team may be unblinded. Productions of outputs related to the analyses of the exploratory endpoints will be done only in case of positive recommendation from the IDMC, as needed. The IDMC will first share recommendation(s) based on the results of the interim efficacy analyses to the Firewall Team and jointly discuss results, as needed, for final Sponsor decision of unblinding according to the protocol, keeping all individuals involved in the study conduct blinded to preserve its integrity. If the study is futile or if EFS is detrimental at the IA, IDMC may recommend early stop of the study providing an observed lack of efficacy and/or futility putting the patients at risk when continuing the study.

For the primary efficacy endpoint, a group-sequential design with α -spending according to Lan-DeMets with O'Brian-Fleming-like boundaries will be used to control the type I error rate. The observed number of EFS events as assessed by the BIRC at the time of the interim analysis will be used to recalculate the exact efficacy and futility boundaries to be used for the interim analysis as well as for the primary analysis (see also Table 3).

If the null hypothesis H_0^{EFS} of the primary efficacy endpoint EFS can be rejected, the null hypothesis H_0^{OS} of the secondary efficacy endpoint OS will be confirmatory tested by a group-sequential design with α -spending according to Lan-DeMets with O'Brian-Fleming-like boundaries to control for the type I error rate. The observed number of OS events at the time of the interim analysis will be used to recalculate the exact efficacy boundaries to be used for this interim analysis as well as for the further planned analyses (see also Table 3).

6.3 Primary Analysis

The primary analysis will be triggered once 429 EFS events across both arms (as assessed by the BIRC) are observed. This is an event driven analysis and monitoring of the number of events will be done throughout the study. The cutoff date will be determined prospectively based on an event projection as the date when approximately 429 EFS events will be reached. In case the observed number of EFS events is >4.5% below the planned number (<410), the PA cut-off date will be revised prior to the conduct of the analysis, based on blinded information on the number of EFS events only, to include at least 410 EFS events into the primary analysis.

The primary intent of this analysis is to demonstrate that xevinapant + CRT prolongs EFS as assessed by the BIRC versus placebo + CRT in case this has not been demonstrated at the interim analysis yet. The observed numbers of EFS events at the interim and primary analysis will be used to recalculate the exact efficacy and futility boundaries (see also Table 3).

If the null hypothesis H_0^{EFS} of the primary efficacy endpoint EFS can be rejected at the interim or primary analysis and the null hypothesis H_0^{OS} of the secondary efficacy endpoint OS was not rejected at the interim analysis, the null hypothesis H_0^{OS} of the secondary efficacy endpoint OS will be confirmatory tested by a group-sequential design with α -spending according to Lan-DeMets with O'Brian-Fleming-like boundaries to control for the type I error rate. The observed number of OS events at the time of the primary analysis will be used to recalculate the exact efficacy boundaries to be used for the primary analysis as well as for the final analysis (see also Table 3).

In case the null hypothesis for EFS can already be rejected at an EFS interim analysis (IA) and the Sponsor decides to unblind the study, confirmatory analysis of EFS is completed with the EFS IA, and subsequent OS IAs will be triggered by the number of OS events.

Other secondary efficacy endpoints and exploratory endpoints will be analyzed without any type I error adjustment. All provided p-values for these analyses will be exploratory.

6.4 Further OS Analyses

A fourth interim analysis for OS will be triggered once 309 OS events are observed across arms. in case there is an increase of at least 39 OS events compared to the event count of the previous interim analysis (~10% increase of information fraction) but not later than 12 months after the previous interim analysis cut-off date. Only endpoints affected by longer follow-up will be analyzed.

The final analysis will be triggered once 386 OS events are observed across both arms (assumed to be 65 months after the first participant was randomized) or the last on-study participant has either reached the 60-month post-randomization follow-up visit or prematurely discontinues, whichever happens first. Only endpoints affected by longer follow-up will be analyzed.

The primary intent of these analyses is to demonstrate that xevinapant + CRT prolongs OS versus placebo + CRT.

If the null hypothesis H_0^{EFS} of the primary efficacy endpoint EFS can be rejected at interim or primary analysis and the null hypothesis H_0^{OS} of the secondary efficacy endpoint OS was not rejected at the interim analysis nor the primary analysis, OS will be confirmatory tested by a group-sequential design with α -spending according to Lan-DeMets with O'Brian-Fleming-like boundaries to control for the type I error rate at the time of final analysis. The observed number of OS events at interim, primary and final analysis will be used to recalculate the efficacy boundaries for H_0^{OS} (see also Table 3).

7 Changes to the Planned Analyses in the Clinical Study Protocol

The primary HRQoL Analysis will focus on the change from baseline at end of combination therapy and the completion of investigational therapy rather than evaluating non-inferiority at Month 12 as stated in Section 3 of the study protocol. Data from assessments after completion of investigational therapy will be presented purely descriptively. The rationale for this approach is that the assessments during the on-treatment period are expected to reflect changes in HRQoL due to side effects of the study treatment, whereas a substantial proportion of missing data is expected at later timepoints such as Month 12, because PRO assessments are not continued after an EFS event.

No sensitivity/supportive analyses (except DoR by investigator assessment) will be performed for the secondary efficacy endpoint duration of response (DoR) due to the reason that the analysis of DoR is not based on the ITT and must be seen itself as a supportive analysis. For this reason, DoR will be analyzed by treatment arms but without any between-arm comparisons.

The list of timepoints for the analysis of the proportion of participants with enteral and parenteral feeding (Section 14.3.2 of this SAP) has been revised to match the schedule of assessments for nutritional status in the study protocol.

In case the difference between the ITT and safety sets is less than 5%, demographics and baseline characteristics will only be assessed and summarized by arm in the ITT set using summary tables and figures.

No changes to the planned analysis of the efficacy or safety endpoints are planned due to the impact of Coronavirus disease 2019 (COVID-19) outbreak. Sensitivity analyses may be considered depending on the observed COVID-19 findings.

Additional outputs (summary table and listing) will be generated for a description of the impact by COVID-19 on the study. The number and percentage of participants will be presented for the following findings due to COVID-19:

- Adverse Events (MedDRA SMQ "COVID-19")
- Important protocol deviations
- Missed Visits (including number of missed visits and detailed reason)
- Missed efficacy evaluations (including number of missed efficacy evaluations)
- Drug administration missed doses

Xevinapant TrilynX Debio 1143-SCCHN-301/ MS202359 0006

- Drug administration dose adjustments
- Treatment discontinuation
- Study discontinuation
- Death

A frequency table will be produced for the SAF analysis set to present the number of participants with important protocol deviations related to COVID-19 (categorized by frequency of participants with an important protocol deviation overall as well as by category of protocol deviation and type of protocol deviation).

In addition, important COVID-19 protocol deviations will also be listed.

Outputs related to disposition and exposure will be amended to present reason of treatment/study discontinuations due to COVID-19 and treatment changes due to COVID-19 (if possible).

8 Analysis Sets and Subgroups

8.1 Definition of Analysis Sets

The following analysis sets will be used for the planned analysis of the global study population: the screened set, the intent-to-treat (ITT) set, and the safety (SAF) set.

Screened Set

The Screened set will include all participants having signed the Informed Consent Form (ICF). Unless otherwise specified, this set will be used for disposition (summary and eligibility participant data for the Consort disposition diagram).

Intent-to-Treat Set

The ITT set includes all randomized participants. Participants will be analyzed according to the randomized treatment (assigned arm) assignment following the intention-to-treat principle. The ITT set will be the primary set for all summaries and analyses of efficacy.

Safety Set

The SAF set includes all participants who received any dose of any of the study intervention (xevinapant/matched placebo, cisplatin/carboplatin, IMRT). Any participants who are randomized to the placebo + CRT group but who are incorrectly administered any dose of xevinapant will be analyzed in the xevinapant + CRT group. Any participant randomized to the xevinapant + CRT who incorrectly receives only placebo rather than xevinapant will be analyzed in the placebo group. The SAF set will be used for all safety analyses and baseline characteristics.

Pharmacokinetic Set

The PK set will include all the participants who have undergone at least one PK sample scheduled. The PK set will be used for all PK analyses.

Analyses	Analysis Set			
	Screened Set	ITT Set	SAF Set	PK Set
Participant Disposition	✓			
Demographics and Baseline Characteristics		✓		
Medical/Surgical History		✓		
Prior Medications		✓		
Concomitant/Subsequent Medications		✓		
Surgical Procedures		✓		
Concomitant 5-HT3 receptor antagonist medication		✓		
Compliance and Exposure			✓	
Efficacy: Primary Endpoint		✓		
Efficacy: Secondary Endpoints		✓		
Safety and Tolerability			✓	
Health-Related Quality of Life		✓		
Health Resource Utilization		✓		
Pharmacokinetics (PK)				✓

8.2 Subgroup Definition and Parameterization

Subgroup analyses will be performed on the primary efficacy endpoint EFS (BIRC assessed) as well as on the secondary efficacy endpoints OS, PFS (BIRC assessed), LRC (investigator assessed), DoR (BIRC assessed), CR (BIRC assessed), and for the exploratory endpoint of time to distant metastasis (investigator assessed) as defined below. Subgroup analyses on these efficacy endpoints, as well as the demographic and baseline data, and the safety data, might be performed for specific regions defined below among "Rest of the World", if the data is to be used for regulatory submission purposes based on the interim, primary, or final analysis. All subgroup analyses will be exploratory, no adjustment for multiplicity will be performed.

For the definition of subgroup level, data as documented in the eCRF will be taken. The category "missing" will not be included in any subgroup analysis.

In case of low number of participants within a category (about < 5% of the randomized population), categories will be pooled when meaningful.

The following subgroups based on baseline characteristics will be considered.

8.2.1 Randomization stratification factors (from IWRS)

The following subgroups are relevant for all endpoints listed in Section 8.2.

Region

- North America
- Western Europe (as defined in Appendix 4) (reference level)
- Rest of the World

Primary tumor site

- Larynx
- Other (Oropharynx and Hypopharynx) (reference level)

Lymph node involvement

- N0-1 (reference level)
- N2
- N3

T size

- T4
- Other (T1, T2, T3) (reference level)

8.2.2 Other subgroups

The following subgroups are only relevant for the primary efficacy endpoint EFS (BIRC assessed) and the secondary efficacy endpoint OS.

Age Group 1

- Age < 65 years (reference level)
- Age \geq 65 years

Age Group 2

- Age < 70 years (reference level)
- Age \geq 70 years

Sex

- Male (reference level)
- Female

Race

- Asian
- American Indian or Alaska Native
- Black or African American
- Native Hawaiian or Other Pacific Islander
- White (reference level)
- Other

Ethnicity

- Hispanic or Latino
- Not Hispanic or Latino (reference level)

Note: Race or Ethnicity category "not reported" will be handled as "missing"

Primary tumor site (as recorded in the eCRF):

- Larynx (reference level)
- Hypopharynx
- Oropharynx

Eastern Cooperative Oncology Group Performance Status (ECOG-PS)

- 0 (reference level)
- ≥1

American Joint Committee on Cancer (AJCC) cancer staging

- III (reference level)
- IVA
- IVB

Alcohol

- current use
- no current use (reference level)

Smoking

- current use (reference level)
- history of use
- no history of use

8.2.3 Analyses in Asian Participants

In order to satisfy requirements of the Japanese Pharmaceuticals and Medical Devices Agency as well as the requirements for an ethnicity report, a subset of data summaries will be produced for each of the countries Japan, Korea, Taiwan compared to the respective complementary set by treatment group and East Asian (pooled including Japan, China, Taiwan and Korea). These will include summaries of:

- Participant disposition
- Participants randomized vs treated
- Analysis sets
- Demographic characteristics
- Disease history
- Subsequent anti-cancer drug treatments
- Primary Endpoint: Event free survival (EFS),
- Secondary Endpoints: overall survival (OS), progression-free survival (PFS), local regional control (LRC), objective response (OR), complete response (CR), duration of response (DoR), proportion of subjects with radical salvage surgery, time to subsequent systemic cancer treatments and HRQoL.
- Treatment exposure
- Adverse events (overall, related, grade ≥ 3 , related grade ≥ 3 , serious, leading to death, related leading to death)

In order to meet the requirement of regulatory consultation and submission to the Chinese National Medical Products Administration, more detailed information on the analyses in Chinese participants are described in Appendix 8.

9 General Specifications for Data Analyses

All statistical analyses will be conducted using SAS® for Windows, Release 9.4 or higher (SAS® Institute Inc., Cary, NC, USA). All outputs will be generated in Rich Text Format (RTF) from Microsoft Word and combined pdf file formats. Further programming specifications can be found in the mock shells.

Unless otherwise specified, summaries will be presented for each treatment arm (labelled xevinapant + CRT and Placebo + CRT) and overall (labelled Total, when appropriate). Unless stated otherwise, participant data listings will be sorted by treatment arm (xevinapant + CRT and Placebo + CRT), participant number, and assessment date (and time).

Unless otherwise specified, continuous variables will be summarized using descriptive statistics, i.e., the number of participants with non-missing values (n), mean, standard deviation, median, 25th percentile (Q1) and 75th percentile (Q3), minimum, and maximum.

Qualitative variables will be summarized by frequency counts and percentages. Unless otherwise stated the calculation of proportions will be based on the number of participants of the analysis set of interest. Therefore, counts of missing observations will be included in the denominator and presented as a separate category.

Descriptive statistics by nominal visit or time point, e.g., for laboratory measurements, will include only data from scheduled visits. Unscheduled visits will be included in the derivation of baseline or worst on-treatment values.

9.1 Data handling after Cut-off Date

Data after the data cut-off date do not undergo the cleaning process. The only exceptions are the date of death and the date last known to be alive from the eCRF.

Data obtained after a cut-off will not be displayed in any listings or used for summary statistics, e.g., laboratory values of samples taken after data cut-off, AE with onset date after data cutoff, etc. will not be included in any analysis or listing.

These rules will be applied to all analyses performed for the interim analyses and primary analysis. For the final analysis no cut-off date will be applied: the analysis will be performed only after all the data have been collected, fully cleaned and the database has been locked.

9.2 Definition of Baseline and Change from Baseline

For efficacy analyses, baseline will be defined as the last non-missing measurement prior to randomization. If no such value is available, the last measurement prior to the first study treatment will be used as the baseline measurement.

For safety analyses, the last non-missing measurement prior to the first study treatment will serve as the baseline measurement.

If an assessment that is planned to be performed before randomization, or study treatment per protocol is performed on the same day as the randomization or start of study treatment, respectively, but the assessment time is not available, it will be assumed that it was performed prior and will be considered for derivation of baseline.

If a scheduled pre-dose measurement actually occurred post-dose, then the corresponding measurement will be analyzed similar to an unscheduled post-dose measurement.

If both central and local labs are collected, the baseline will be derived based only on the central lab collected data.

Absolute and percent changes from baseline are defined as

- absolute change = visit value baseline value
- percent change = 100 * (visit value baseline value) / baseline value

9.3 First Dose Date

First dose date is defined as the day of **first** administration of any study intervention (xevinapant/matched placebo, chemotherapy (cisplatin and/or carboplatin) or IMRT treatment (background radiotherapy)).

It is expected that on C1D1 xevinapant or matched placebo is given first and followed by IMRT. First dose of chemotherapy is scheduled on C1D2, after xevinapant/matched placebo dose and before IMRT.

9.4 Last Dose Date

Last dose date is defined as the latest of last administration of any study intervention (xevinapant/matched placebo, chemotherapy (cisplatin and/or carboplatin) or IMRT).

9.5 Definition of On-treatment Period

The on-treatment period is defined as any time from first dose date until the last dose date + 30 days.

9.6 Study Day / Study Treatment Day

Day 1 is the day of randomization/start of study treatment, the day before is Day -1 (no Day 0 is defined). Study day / Study treatment day is defined relative to Day 1.

9.7 Definition of Duration and 'Time Since' Variables

Durations in days will be calculated by the difference of start and stop date + 1 (e.g., survival time (days) = date of death – date of randomization + 1) if not otherwise specified.

Treatment duration of each study intervention (xevinapant/matched placebo, chemotherapy (cisplatin and/or carboplatin) or IMRT) is calculated based on first dose date and last dose date of the respective study intervention component as ceiling (last dose date – first dose date + x) divided by 7 for display in weeks, where x is equal to 8 for xevinapant/matched placebo and chemotherapy and x is equal to 3 for IMRT.

The overall treatment duration is defined as max(xevinapant/matched placebo treatment duration, CT treatment duration, IMRT treatment duration).

The time since an event (e.g., time since first diagnosis) will be calculated as reference date minus date of event.

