xevinapant vs placebo, when added to CRT	Extent of exposure of the different treatment agents (i.e., xevinapant or matched placebo, radiotherapy, chemotherapy) including: Treatment duration. Number of cycles. Actual dose. Dose intensity. Relative dose intensity. Incidence of treatment interruption. Incidence of treatment reduction. Incidence of treatment discontinuation.		Safety	- From first study treatment dose to EOT.
To compare the health-related quality of life of xevinapant vs placebo when added to CRT using patient-reported outcome questionnaires	Changes from baseline in: CCI .	Xevinapant is non-inferior for CCI at Month 12 post-randomization in previously untreated patients with LA-SCCHN compared to matched placebo when administered in combination with platinum-based chemotherapy and IMRT.	Intent-to-treat	 From randomization to EOS. At baseline, Study Week 10, 20 and months 7, 12, 24, 36, 48 and 60 post-randomization.

Objectives	Endpoints	Hypothesis	Primary Analysis Population	Timeframe/Time Point

4. Study Design

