12.1 Concomitant 5-HT3 Receptor Antagonist

Concomitant 5-HT3 receptor antagonist medications (any medication coded with ATC Level 4 equal to "SEROTONIN (5HT3) ANTAGONISTS") will be summarized overall and by treatment arm for all participants from SAF set who reported renal toxicity (grade 3 or 4) vs. participants who did not report renal toxicity. Renal toxicity grade 3 or 4 includes any participant with at least one post-baseline toxicity grade 3 or 4 for estimated Glomerular Filtration Rate (eGFR) or Creatinine. The following will be summarized:

• Number and percentage of patients with any 5-HT3 receptor antagonist medication.

- Number and percentage of patients by 5-HT3 receptor antagonist medication alone. PT will be used to summarize each medication.
- Number and percentage of patients with any combination of 5-HT3 receptor antagonist medications.

Supportive listings will be provided for patients with and without renal toxicity (grade 3 or 4) who took concomitant 5-HT3 receptor antagonist medication.

13 Study Intervention: Compliance and Exposure

The exposure to xevinapant/matched placebo, cisplatin/carboplatin, and IMRT will be summarized by cycle and overall, by actual treatment arm for all participants from SAF set. The following extent of exposure parameters will be summarized:

- Number of treatment cycles, defined as the number of cycles in the eCRF with non-zero dose administration of xevinapant/matched placebo, cisplatin/carboplatin. No cycle is defined for IMRT.
- Treatment duration (in weeks) is calculated per study intervention component as
 - \circ Chemotherapy treatment duration = (last dose date first dose date + 21)/7 weeks
 - Cisplatin treatment duration = (last dose date first dose date + 21)/7 weeks
 - Carboplatin treatment duration = (last dose date first dose date + 21)/7
 weeks
 - \circ IMRT treatment duration = (last dose date first dose date + 3)/7 weeks

Xevinapant / Placebo treatment duration = (last dose date - first dose date + 8)/7
 weeks

Overall treatment duration is defined as the maximum of xevinapant / placebo treatment duration, chemotherapy treatment duration, and RT treatment duration.

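### SAP Sections 9.7 and 13 define chemotherapy treatment duration differently (+8 with a ceiling versus +21 without), giving 7.1 or 8 weeks against 9.0 weeks for the same three cycles

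*SAP*

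**What the plan says.** SAP Section 9.7 defines the duration of each component from its own first and last dose dates and names the chemotherapy component as cisplatin and/or carboplatin. The calculation is given "as ceiling (last dose date – first dose date + x) divided by 7 for display in weeks". Section 9.7 then fixes the constant for the three components: "where x is equal to 8 for xevinapant/matched placebo and chemotherapy and x is equal to 3 for IMRT". Overall treatment duration is the maximum of the three component durations.

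SAP Section 13 defines the same variables again for the exposure tables. It has "Chemotherapy treatment duration = (last dose date first dose date + 21)/7 weeks", then "Cisplatin treatment duration = (last dose date first dose date + 21)/7 weeks", and the same expression for carboplatin. (The minus sign between the two dates has dropped out in text conversion; the constant is legible.) It also has "IMRT treatment duration = (last dose date first dose date + 3)/7 weeks" and plus 8 for xevinapant or placebo. None of these formulas has a ceiling. Overall duration is again the maximum over components.

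In Protocol Table 3-1 and SAP Table 1, "Treatment duration" is the first of eight exposure items listed as a secondary endpoint under the safety and compliance objective. SAP Section 7, which lists changes to the planned analyses, does not mention this difference.

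**The concern.** The same variable, built from the same two dates and reported in the same unit, has two constants 13 days apart. One of the two definitions also has a ceiling whose placement is unclear. The sections match for xevinapant or placebo (plus 8) and for IMRT (plus 3), so chemotherapy is the only component whose constant conflicts.

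Two programmers who each followed the SAP faithfully could therefore produce exposure tables that do not match. What is at stake is the reported chemotherapy duration, and in some participants the overall treatment duration derived from it.

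**Working it through.** The SAP states no numerical duration, so there is no published figure to reproduce. The check applies both formulas to the protocol schedule.

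**Inputs**
- Chemotherapy: Day 2 of each 3-week cycle, at most three cycles (Protocol 6.1.2.2). Study days are 2, 23 and 44 (Protocol Table 1-1).
- Xevinapant or placebo: Days 1 to 14 of each 3-week cycle, six cycles (Protocol 6.1.2.1). The last dose of cycle 2 falls on study day 35, of cycle 3 on day 56, and of cycle 6 on day 119.
- IMRT: five fractions a week for seven weeks (Protocol 6.1.2.3). Assuming a Monday start with no interruption, it runs from day 1 to day 47.
- Constants: chemotherapy +8 in SAP 9.7 and +21 in SAP 13; xevinapant or placebo +8 and IMRT +3 in both.

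**Chemotherapy duration, (last − first + constant) / 7**

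| Cycles given | Last − first | 9.7, ceiling on days | 9.7, ceiling on weeks | Section 13 |
|---|---|---|---|---|
| 1 | 0 | 8/7 = 1.14 | 2 | 21/7 = 3.00 |
| 2 | 21 | 29/7 = 4.14 | 5 | 42/7 = 6.00 |
| 3 | 42 | 50/7 = 7.14 | 8 | 63/7 = 9.00 |

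Read literally, the ceiling in 9.7 acts on a whole number of days and does nothing, so the gap is always 21 − 8 = 13 days, or 1.86 weeks. For three cycles, 9.7 is then 1.86/9.00 = 21% lower. With the ceiling on weeks, the gap is one week in each row, which is 1/9 = 11% for three cycles.

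**What the constants appear to be for**
- Xevinapant or placebo, one cycle: 14 − 1 + 8 = 21 days, a full cycle. Six cycles: 119 − 1 + 8 = 126 days = 18.0 weeks.
- IMRT, full course from a Monday: 47 − 1 + 3 = 49 days = 7.0 weeks.
- Chemotherapy, one infusion: 0 + 21 = 21 days, a full cycle; 0 + 8 = 8 days is not.

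The two undisputed constants each round the exposure up to the end of its dosing interval. For an infusion given once every three weeks, only 21 does the same.

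**Overall duration (maximum over components)**
- Six xevinapant or placebo cycles: 18.0 weeks under both formulas.
- Xevinapant or placebo on schedule through cycle 3 Day 14: 56 − 1 + 8 = 63 days = 9.0 weeks. On-schedule chemotherapy reaches at most 9.0 weeks even with +21, so overall duration is the same.
- Xevinapant or placebo stopped after cycle 2 Day 14, with three infusions and full IMRT: xevinapant or placebo (35 − 1 + 8)/7 = 6.0 and IMRT 7.0. Chemotherapy is 7.14 under 9.7 (literal reading) and 9.00 under Section 13, so overall duration is 7.14 or 9.00 weeks.
- The same early stop with only two infusions: chemotherapy is 4.14 or 6.00 weeks. Both are below the 7.0 weeks of IMRT, so overall duration does not change.

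**The case against.** The strongest reply is that little depends on this. Section 13 is the dedicated exposure section and writes the +21 formula out three times, so a programmer would probably follow it. Treatment duration has no hypothesis attached and is only summarised. That reply stands as a limit on importance. It does not remove the conflict, because the SAP states no order of precedence and 9.7 is the general definition of duration.

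A second reply is that the gap depends on how the ceiling is read. This also stands: 7.1 weeks is the literal result and 8 weeks the alternative. Neither equals 9.0, so the sections disagree either way.

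A third reply is that neither section says a duration must run to the end of the dosing interval. That is correct. The principle is inferred from the constants that agree, so calling the 9.7 constant the outlier is a reasonable inference and not something the SAP states.

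A reader might also infer that overall treatment duration is generally affected, or that safety results shift. The documents do not support either. Overall duration is identical for anyone taking xevinapant or placebo on schedule through cycle 3 Day 14 with chemotherapy on schedule. SAP 13 computes dose intensity from cycle duration and relative dose intensity from planned amounts, not from this variable. The on-treatment window for adverse events is the last dose date plus 30 days (SAP 9.5).

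**Conclusion.** The inconsistency is real. For a participant with three on-schedule cycles, chemotherapy duration is 7.1 weeks (or 8) under SAP 9.7 and 9.0 weeks under SAP 13. For one cycle it is 1.1 (or 2) against 3.0. It touches the chemotherapy duration of every participant given chemotherapy. Overall duration is affected mainly when xevinapant or placebo stops before cycle 3 Day 14, or when chemotherapy is delayed.

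The consequences are limited to descriptive exposure reporting. EFS, OS, control of the type I error, dose intensity and the window for treatment-emergent adverse events are unaffected. The figures assume chemotherapy on study days 2, 23 and 44; the IMRT check also assumes a Monday start. That 21 is the intended constant is likely but needs confirmation from the SAP authors. This is a minor correction, best made before the exposure tables are programmed.

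**What to change.** In SAP 9.7, subject to the authors' confirmation, set the constant to 21 for chemotherapy (cisplatin and carboplatin), and keep 8 for xevinapant or placebo and 3 for IMRT. Either remove the ceiling or state once whether it applies and to which quantity. Then replace the formulas in Section 13 with a reference to 9.7, so that only one definition exists. Changing the number alone and pointing Section 13 to 9.7 would carry the unclear ceiling into the exposure tables.

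The cost is a small edit to two SAP sections. No protocol change or new data collection is needed, and no treatment rule is involved.
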